8.2.1.1 Part 1: Dose Escalation Cohort primary endpoint

For Part 1, the primary endpoint of MTD will be determined according to Section 6.2.3.

8.2.1.2 Part 2: Child Pugh B Expansion Cohort primary endpoint

For Part 2: Child Pugh B Expansion Cohort, the primary endpoint is safety of the combination in patients with Child Pugh B liver function as measured by rate of grade ≥3 AE (CTCAE v. 4.03) assessed as at least possibly related to sorafenib, nivolumab, or the combination of therapies. Adverse events will be graded using NCI CTCAE v.4.03 (https://ctep.cancer.gov/). Relationship to sorafenib, nivolumab, or combination will be adjudicated by the treating investigator and/or Study Chair.

This is a pilot study. For Part 2, an acceptable rate of grade ≥3 treatment-related AE would be ≤ 50% based upon rate of treatment-related grade ≥3 AE of 24.5% of Child Pugh B7-8 HCC patients treated with nivolumab in the CheckMate 040 Child Pugh B cohort,³⁸ and 28% of Child Pugh B7-9 HCC patients treated with nivolumab in a retrospective institutional cohort,³⁹ along with rates of grade 3-4 treatment-related AE of 30-36% in Child Pugh B7-9 HCC in the GIDEON registry.⁴⁰

With an expected sample size of 12 patients with Child Pugh B7-9 HCC treated in Part 2, the 95% confidence interval (CI) for determining the rate of grade \geq 3 treatment-related AE if the actual rate is 50% will be (0.22, 0.78). If the actual rates are 30%, 40% or 60%, the 95% CI will be (0.07, 0.60), (0.14, 0.70) and (0.30, 0.86) respectively.

If the Child Pugh B Expansion Cohort end of enrollment date of 30 April 2022 is reached before completion of enrollment of n=12, rates of grade ≥3 treatment-related AE will be described along with 95% CI according to the sample size accrued at time of discontinuation (Table 8.2.1-1).

Table 8.2.1-1. Sample Size of Child Pugh B Expansion Cohort for Estimating Rate of Grade ≥3 TRAE.

Sample size in Child Pugh B Expansion Cohort	Actual rate of Grade ≥3 TRAE	95% CI
	30%	0.0, 0.71
6	40%	0.0, 0.71
O	50%	0.10, 0.90
	60%	0.30, 1.0
	30%	0.0, 0.55
0	40%	0.0, 0.71
8	50%	0.15, 0.85
	60%	0.29, 0.96
	30%	0.02, 0.58
10	40%	0.10, 0.71
10	50%	0.19, 0.81
	60%	0.30, 0.90
	30%	0.07, 0.60
12	40%	0.14, 0.70
12	50%	0.22, 0.78
	60%	0.30, 0.86

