In the SHARP study, treatment-related adverse events occurred in 80% of patients in the sorafenib group by comparison with 52% in the placebo group.² Grade 3 toxicities included diarrhea (8%), hand-foot skin reaction (8%), hypertension (2%), and abdominal pain (2%) in the treatment group. Grade 3 or 4 hypophosphatemia (4%) and thrombocytopenia (4%) were also more common in patients treated with sorafenib. In the Asian randomized, placebo-controlled Phase III study, the most common Grade 3 and 4 toxicities were hand-foot skin reaction (10.1%), diarrhea (6%), hyperbilirubinemia (3.4%), and fatigue (3.4%) with the use of sorafenib.¹ The preceding Phase II study of sorafenib in HCC included 28% of patients with Child-Pugh class B cirrhosis; subgroup analysis in this cohort with greater degree of hepatic impairment showed higher rates of hyperbilirubinemia and encephalopathy developing on study by comparison with patients with Child-Pugh class A.^{12,13}

As of 31-December 2015 approximately 70,897 patients have been exposed to sorafenib in company-sponsored interventional clinical trials, non-interventional studies and investigator-sponsored studies for which Bayer has provided grants. The cumulative post-marketing exposure, excluding above mentioned clinical studies, since 2005 is estimated to be 440,109 patients.

Please refer to the current version of the sorafenib IB for the complete list of observed adverse events seen in Phase III studies.

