6.6 Blinding

This is an open-label study. No blinding will be performed.

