- 2. Nivolumab will be administered at flat dose of 240 mg IV over 30 minutes every 14 days (-2 to +3 days) on D1 and D15 each cycle starting on C1D1. In Part 2 and with Study Chair approval, patients meeting criteria in Section 6.5 may switch to monthly dosing of nivolumab starting on or after C4D1 (-4 to +6 days) provided no uncontrolled or grade >2 immune related toxicity. A note to file must be included in study chart documenting Study Chair or designee approval. For patients who switch to monthly dosing on or after C4D1, the D15 visit and other assessments may be omitted if not clinically-indicated.
- 3. Cross-sectional imaging with CT or MRI abdomen plus pelvis (including triphasic/multiphase liver) and CT chest with or without contrast is required at screening and every 8 weeks ±14 days until end of treatment; ; at SFFUV1, imaging does not need to be repeated if performed within 28 days prior (±28 day window). Imaging may be performed more frequently if clinically indicated to evaluate for progression or toxicity. RECIST 1.1 measurements should be performed by a radiologist or qualified investigator at each time point.
- 4. Complete blood count and differential (CBCD), metabolic panel including liver and kidney function and electrolytes (see Section 7.3.6 for individual tests required), and PT/INR should be obtained as standard of care safety monitoring before every nivolumab infusion.
- 5. C1D1 blood tests and urinalysis do not need to be repeated if performed within 3 days before C1D1 during screening.
- 6. Perform on women of childbearing potential only at screening within 28 days, 24 hours prior to each nivolumab infusion (including C1D1), and at safety follow up visits. If urine pregnancy results cannot be confirmed as negative, a serum pregnancy test will be required.

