7.3.6 Liver function assessment

The investigator or qualified designee will assess liver function by Child Pugh score (see Appendix 14.3) at the time points specified in the Schedule of Procedures (Section 7.1).

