7.4 Assessing and reporting adverse events (AE)

All subjects who receive at least one dose of study treatment will be evaluable for safety from the time of informed consent until 100 days after last dose of protocol therapy or the start of a new anti-cancer therapy after study discontinuation, whichever is earlier. Any serious adverse events (SAE) occurring later than 100 days after the last dose of protocol therapy or after start of new anti-cancer therapy also should be recorded and reported if assessed as at least possibly related to study drug or a protocol-specified procedure. All observations pertinent to the safety of the study treatment will be recorded and included in the final report.

Safety variables include the following: AEs, laboratory changes (complete blood counts, electrolytes, chemistry, and coagulation) if determined clinically significant by treating investigator and/or Study Chair, changes in vital signs (blood pressure, heart rate, respiratory rate, and temperature), and in some instances, changes in imaging findings if indicative of a safety event.

All AEs whether considered drug-related or not, will be recorded in case report forms in the OnCore® CTMS including Grade, attribution to one or both study drugs, other attribution(s), start/stop dates, and whether serious and/or unexpected. For all events, the relationship to treatment and the intensity of the event will be determined by the investigator. This trial will use the NCI CTCAE v.4.03 (https://ctep.cancer.gov/) for assessment of toxicity and SAE reporting with regard to toxicity grade. Investigators should refer to the Safety Information section of the current IB for sorafenib and nivolumab, including the DCSI (development core safety information), for the expected side effects of the study drugs.

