7.4.1 AE and SAE definitions

7.4.1.1 Definition of adverse event (AE)

An Adverse Event (AE) is defined as any new untoward medical occurrence or worsening of a preexisting medical condition in a clinical investigation participant administered study drug and that does not necessarily have a causal relationship with this treatment. An AE can therefore be any unfavorable and unintended sign (such as an abnormal laboratory finding determined to be of clinical significance by the treating investigator or Study Chair), symptom, or disease temporally associated with the use of investigational product, whether or not considered related to the investigational product.

The causal relationship to study drug is determined by a physician and should be used to assess all adverse events (AE). The casual relationship can be one of the following:

- Related: There is a reasonable causal relationship between study drug administration and the AE.
- Not related: There is not a reasonable causal relationship between study drug administration and the AE.

Conditions that started before signing of informed consent and for which no symptoms or treatment are present until signing of informed consent are recorded as medical history (e.g. seasonal allergy without acute complaints). Conditions that started before signing of informed consent and for which symptoms or treatment are present after signing of informed consent, at unchanged intensity, are recorded as medical history (e.g. allergic rhinitis). Conditions that started or deteriorated after signing of informed consent will be documented as AEs.

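### The Part 2 primary safety rate leaves out hepatic events judged unrelated, and no analysis of on-treatment Child Pugh or liver-test change is planned beside it

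*Combined protocol and SAP*

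**What the plan says.** The Part 2 primary objective (Section 2.1) is safety in Child Pugh B liver function. Section 8.2.1.2 measures it by grade ≥3 adverse events "assessed as at least possibly related to sorafenib, nivolumab, or the combination of therapies". A rate of at most 50% is called acceptable, and 12 patients are expected. On attribution, the section says: "Relationship to sorafenib, nivolumab, or combination will be adjudicated by the treating investigator and/or Study Chair". Section 6.6 adds: "This is an open-label study. No blinding will be performed".

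Laboratory values pass an earlier filter. In Section 7.4, laboratory changes are safety variables "if determined clinically significant by treating investigator and/or Study Chair". In Section 7.4.1.1, the adverse event definition takes in "an abnormal laboratory finding determined to be of clinical significance by the treating investigator or Study Chair".

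Objective liver data are collected throughout. Under Section 7.3.6 the investigator "will assess liver function by Child Pugh score". The Part 2 schedule (Section 7.1.2) places this at screening, days 1 and 15 of cycles 1 and 2, day 1 of every later cycle, and both safety visits. Blood count, chemistry and PT/INR "should be obtained as standard of care safety monitoring before every nivolumab infusion". Within Section 8, liver function appears only as a baseline characteristic in the exploratory analyses (8.2.3 to 8.2.3.3).

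Three further provisions matter:
- Section 7.4 has all adverse events recorded whatever their attribution, and Section 8.2.2.1 summarises them by organ class, term, grade and relationship.
- Section 8.1.2 drops from the safety analyses patients who stop before completing cycle 1 for underlying liver disease judged neither progression nor treatment toxicity. Section 5.3.2 replaces patients who are not evaluable for safety.
- Section 7.4 makes anyone with one dose of study treatment evaluable for safety.

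**The concern.** In Child Pugh B cirrhosis, drug-induced liver injury and progression of the liver disease can look alike, so attribution is least secure for the events that matter most here. The protocol identifies the hazard itself: Section 1.3.2 reports that Child Pugh B patients on sorafenib had "higher rates of hyperbilirubinemia and encephalopathy developing on study by comparison with patients with Child-Pugh class A". The cohort has no control group against which to check attribution.

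The primary rate could therefore read as acceptable while liver function falls, with no planned table to show the fall. Acceptable safety in Part 2 is one of the conditions that Section 8.2.2.3 sets for considering a larger study, so the gap bears on a decision.

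**Working it through.** **1. The plan's own intervals.** Take n = 12 and x = the whole number nearest 12 × rate. The formula is p ± 1.96 × √(p(1−p)/n), with p = x/n. For a 50% rate, x = 6: 0.5 ± 1.96 × √(0.25/12) = 0.5 ± 0.283 = (0.217, 0.783), against the stated (0.22, 0.78). For 30%, 40% and 60% (x = 4, 5, 7) the results are (0.067, 0.600), (0.138, 0.696) and (0.304, 0.862). All four n = 12 intervals are reproduced.

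**2. Weight of one patient.** 1/12 = 8.3 points.

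| Patients counted | Rate | Exact 95% CI | Meets ≤50%? |
|---|---|---|---|
| 5/12 | 41.7% | 0.15-0.72 | yes |
| 6/12 | 50.0% | 0.21-0.79 | yes |
| 7/12 | 58.3% | 0.28-0.85 | no |

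From 6/12, one uncounted patient decides the result; from 5/12, two do.

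**3. Where a hepatic event ends up under the plan.**

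| Event | Primary rate | All-AE/SAE summary (8.2.2.1) |
|---|---|---|
| Grade ≥3, declared an AE, judged at least possibly related | counted | counted |
| Grade ≥3, declared an AE, judged unrelated | not counted | counted |
| Laboratory or Child Pugh decline never declared an AE | not counted | not counted |
| Patient stops in cycle 1 for liver disease judged not treatment-related (8.1.2) | patient removed | patient removed |

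Rows 3 and 4 are the true losses.

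**4. Possible undercount in the primary rate.** The documents give no rate of misattribution, so both inputs are assumed. Let H be the number of patients with a grade ≥3 hepatic event and m the share wrongly judged unrelated. Undercount ≤ H × m. With H = 3 and m = 10% to 50%, this is 0.3 to 1.5 patients, or 0.3/12 = 2.5 to 1.5/12 = 12.5 points. It is an upper bound because the rate is read per patient: a reclassified event lowers it only if that patient has no other related grade ≥3 event.

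**5. Chance of meeting the limit.** Suppose the rate with all such events counted is 60%. Under a binomial with n = 12, the chance of 6 or fewer is 0.335. If 10, 20 or 30 percentage points of patients have their only qualifying event called unrelated, the binomial rate is 50%, 40% or 30%, and the chance becomes 0.613, 0.842 or 0.961. These rates are also assumed.

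**6. Effect of the cycle-1 exclusion.** Suppose 13 patients are treated, 12 are evaluable with 6 related events, and the thirteenth stopped in cycle 1 with a grade ≥3 hepatic event judged unrelated. The planned rate is 6/12 = 50.0%. With the thirteenth in the denominator it would be 6/13 = 46.2%, so the exclusion does not by itself flatter the primary rate. What is lost is the event from the all-cause picture, which would be at least 7/13 = 53.8%.

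**The case against.** A reader might infer that hepatic harm put down to cirrhosis is counted nowhere, and that the liver data are never used. The documents do not support either reading. Section 7.4.1.1 makes worsening of a pre-existing condition an adverse event, Section 7.4 records it regardless of attribution, and Section 8.2.2.1 tabulates it. A grade 3 encephalopathy blamed on cirrhosis would be visible there. Baseline liver function does enter the exploratory analyses.

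Other safeguards exist. The clinical-significance filter applies to laboratory findings, not to clinical events. New ascites, encephalopathy and varices are documented during treatment and into safety follow-up (Section 7.2.5.2), and potential drug-induced liver injury must be handled as serious (Section 7.4.1.2). The threshold of possible relatedness is low. Appendix 11 (Section 3.1) defines unrelated as clearly not related and has a committee review attribution weekly. Blinding would not help, since every patient receives both drugs.

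All of this stands, and it confines the concern to rows 2 to 4 of the second table. It does not remove it. Section 7.4.1.1 offers only a related/not related choice, so the low threshold is not applied uniformly. Documentation of decompensation has no analysis attached. No summary of declared events can show a decline that nobody declared, or a patient taken out of the analysis set.

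It is also fair to say that the added tables would not change the primary rate. They are not meant to: the 50% limit was set against treatment-related rates (24.5%, 28% and 30-36%), and an all-cause rate should not be held to it.

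**Conclusion.** The concern holds in limited form. Hepatic events judged unrelated are outside the primary rate but inside the secondary summary when declared. Undeclared on-treatment decline in Child Pugh score or liver tests is reported nowhere. Some early liver-related stops leave every safety analysis, in conflict with the evaluability statement in Section 7.4.

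One patient is 8.3 points, enough to cross the limit from 6/12. How many patients would be affected cannot be derived from the documents; the 2.5-12.5 point range is an upper bound resting on the assumed 3 of 12 and 10-50%. It should not be read as a forecast that misattribution will occur. This is an inexpensive improvement to a descriptive pilot, not a reason to replace its primary endpoint.

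**What to change.** Keep the primary endpoint and its benchmark. Add to Section 8.2.2.1, for all Part 2 patients who received at least one dose of study treatment (the Section 7.4 definition, not the Section 8.1.2 set) and regardless of attribution:

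1. Change in Child Pugh score and class from C1D1, with n/N and an exact 95% CI for a worsening defined before the data are tabulated. One example is a rise of at least 2 points or new class C; the cut-off is the sponsor's choice. The two parts do different work: under Appendix 3, a patient at 7 points who rises by 2 is still class B, while one at 9 who rises by 1 becomes class C.
2. Worst post-baseline CTCAE grade shift for AST, ALT, bilirubin, albumin, INR and platelets, from every collected value. Shift from baseline is needed because Part 2 admits AST and ALT up to 8 × ULN (Section 5.1.1), above the 5 × ULN that Section 6.2.3.2 labels Grade 3.
3. The per-patient all-cause grade ≥3 rate with exact CI, printed beside the primary rate. This mainly makes explicit what Section 8.2.2.1 already covers.

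Reconcile Sections 7.4 and 8.1.2, and list every patient excluded or replaced, with the reason.

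The cost is three tables and a listing from data already on the visit schedule; no visit or sample is added. The downside is that these rates will be higher than the primary rate and will include progression of cirrhosis, which cannot be separated without controls. The report should say so.

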8.4.2 Part 2: Child Pugh B Expansion Cohort sample size

The Part 2 expected evaluable sample size is n=12 patients.

9. Data handling and quality assurance

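### Table 8.2.1-1 and the n=12 sentence give 95% intervals for rounded patient counts instead of the stated rates, and no interval method is named for the Part 2 primary endpoint

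*Combined protocol and SAP*

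**What the plan says.** Section 8.2.1.2 defines the Part 2 primary endpoint as safety "as measured by rate of grade ≥3 AE (CTCAE v. 4.03) assessed as at least possibly related to sorafenib, nivolumab, or the combination of therapies". It takes 50% as the highest acceptable rate, citing 24.5% and 28% from two nivolumab cohorts and 30-36% from a sorafenib registry.

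Precision is then described "With an expected sample size of 12 patients with Child Pugh B7-9 HCC treated in Part 2". At 50% the interval is given as (0.22, 0.78). For the other rates: "If the actual rates are 30%, 40% or 60%, the 95% CI will be (0.07, 0.60), (0.14, 0.70) and (0.30, 0.86) respectively". If accrual closes on the calendar date before 12 patients are enrolled, "rates of grade ≥3 treatment-related AE will be described along with 95% CI according to the sample size accrued at time of discontinuation". Table 8.2.1-1 gives intervals for n=6, 8, 10 and 12, with rows labelled as the actual rate: 30%, 40%, 50% and 60%.

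Section 8.4.2 adds only this: "The Part 2 expected evaluable sample size is n=12 patients". Neither Section 8.2.1.2 nor Section 8.2.2 says how a 95% interval for a proportion will be computed.

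**The concern.** Two oddities show without any calculation. At n=6 the 30% and 40% rows carry the same interval, (0.0, 0.71). And the upper limit for a 30% rate goes up as patients are added: 0.55 at n=8, 0.58 at n=10, 0.60 at n=12. Intervals for one fixed rate should tighten as n grows.

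These are the only precision figures for the primary endpoint. A reader who asks what 12 or fewer patients can show about a 30% toxicity rate is given the interval for 33% or 25%. The figures also point to the Wald formula. If that were carried into the final report, its upper limits would be too low at low event counts, which is the reassuring direction for a toxicity rate.

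**Working it through.** **Inputs.** Sample sizes, rates and printed limits are from Section 8.2.1.2 and Table 8.2.1-1. The level is 95%, two-sided, z = 1.96.

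**Formula tested (Wald).** p ± 1.96 × √(p(1−p)/n), cut at 0 and 1.

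**1. Reproduce a printed figure.** n=12, 50%: 0.5 ± 1.96 × √(0.25/12) = 0.5 ± 0.283 = (0.22, 0.78). This matches.

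**2. Try the 30% figure at n=12.**
- Wald at 0.30: 0.30 ± 1.96 × √(0.21/12) = 0.30 ± 0.259 = (0.04, 0.56). Printed: (0.07, 0.60). No match.
- Wilson at 0.30: (0.12, 0.58). Clopper-Pearson with 3.6 events: (0.08, 0.62). No match.
- n × rate = 3.6, which rounds to 4. Wald at 4/12: 0.333 ± 1.96 × √(0.2222/12) = 0.333 ± 0.267 = (0.07, 0.60). This matches.
- Clopper-Pearson at 4/12 is (0.10, 0.65) and Wilson is (0.14, 0.61). Neither matches.

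**3. Repeat for every row.** In nine rows n × rate is not a whole number:

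| n | Label | n × rate | Count | Printed | Wald at label | Wald at count |
|---|---|---|---|---|---|---|
| 6 | 30% | 1.8 | 2/6 | 0.0, 0.71 | 0, 0.67 | 0, 0.71 |
| 6 | 40% | 2.4 | 2/6 | 0.0, 0.71 | 0.01, 0.79 | 0, 0.71 |
| 6 | 60% | 3.6 | 4/6 | 0.30, 1.0 | 0.21, 0.99 | 0.29, 1 |
| 8 | 30% | 2.4 | 2/8 | 0.0, 0.55 | 0, 0.62 | 0, 0.55 |
| 8 | 40% | 3.2 | 3/8 | 0.0, 0.71 | 0.06, 0.74 | 0.04, 0.71 |
| 8 | 60% | 4.8 | 5/8 | 0.29, 0.96 | 0.26, 0.94 | 0.29, 0.96 |
| 12 | 30% | 3.6 | 4/12 | 0.07, 0.60 | 0.04, 0.56 | 0.07, 0.60 |
| 12 | 40% | 4.8 | 5/12 | 0.14, 0.70 | 0.12, 0.68 | 0.14, 0.70 |
| 12 | 60% | 7.2 | 7/12 | 0.30, 0.86 | 0.32, 0.88 | 0.30, 0.86 |

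Seven of the nine match the rounded count on both limits and two match on one. In the other seven rows of the table (all 50% rows and all n=10 rows) the count is whole, so label and count agree.

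Three limits miss even the rounded-count value: n=6, 60% lower (0.30 against 0.2895); n=8, 40% lower (0.0 against 0.0395); n=10, 40% upper (0.71 against 0.7036).

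**4. Does the choice of method matter?** Exact coverage at true rate p is the sum of the binomial probabilities of those counts x whose interval contains p. At n=12:

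| True rate | 24.5% | 28% | 30% | 36% | 40% | 50% | 60% |
|---|---|---|---|---|---|---|---|
| Wald | 82% | 86% | 88% | 93% | 90% | 85% | 90% |
| Clopper-Pearson | 99% | 97% | 98% | 99% | 97% | 96% | 97% |

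At 24.5%, Wald misses 18.1% of the time. In 16.8 of those points the upper limit lies below the true rate.

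**5. A likely result.** For 3/12, Wald gives 0.25 ± 1.96 × 0.125 = (0.005, 0.495) and Clopper-Pearson gives (0.05, 0.57). If the combination had a true rate of 24.5%, 28% or 30%, then 3/12 would be the single most likely count, with probability 0.258, 0.251 or 0.240.

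**The case against.** Several points can fairly be made for the plan.

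- Rounding to whole patients is defensible, because 3.6 events out of 12 cannot be observed. That is true, and the replacement below also uses whole counts. The fault is that the rows are labelled with a different rate and nothing says so.
- The gaps at n=12 are at most about 0.04. The printed upper limits at 30% and 40% are higher than Wald at the label, which is the cautious direction. This stands for n=12. The larger gaps, up to about 0.09 (n=6, 60% lower), are at the fallback sizes.
- The three stray limits may be reading faults in the extracted table, and two differ by only 0.01. This cannot be excluded. The nine mislabelled rows do not depend on them, and the n=12 values are the same in the sentence and the table.
- The coverage at 24.5% sits just past a step. The Wald upper limit for 1/12 is 0.2397, and that count alone supplies 13.4 of the 16.8 points. Coverage is 95% at a true rate of 23.9% and 81% at 24.0%. At 36%, the top of the cited registry range, it is 93%. So 82% is not typical, but at all the other rates in step 4 coverage is still 85% to 93%, below 95%.
- The plan never says that Wald will be used at the end. That is correct, and it is part of the problem, since it says nothing on the method.
- Wald is not too narrow everywhere: at 3/6 it gives (0.10, 0.90), against an exact (0.12, 0.88).
- This is a descriptive pilot. The 50% row at n=12 is right under Wald, and with this version dated 03/09/2022 and accrual closing by 30 April 2022, the table can hardly affect sample size. This limits the weight of the point but does not make the figures right.

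**Conclusion.** The concern holds. Nine of the 16 rows, and the n=12 sentence for 30%, 40% and 60%, describe a rate other than the one on the label. Three limits do not match any consistent rule, and no interval method is named for the primary endpoint. At n=12 the error in the limits is at most about 0.04; at n=6 and n=8 it reaches about 0.09.

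That Wald was used is inferred from the match, not stated. The coverage and 3/12 figures assume that it would be carried into the analysis and that the combination has toxicity rates like those the plan cites for single agents. On that basis the choice of method alone could decide whether the reported interval excludes 50%. The 50% statement refers to no interval bound and early closure is by date, so no formal decision changes. This should be corrected, but it is not a flaw in the design.

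**What to change.** Relabel Table 8.2.1-1 and the n=12 sentence by observed count, and replace the limits with Clopper-Pearson 95% intervals:

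| n | x/n and interval |
|---|---|
| 6 | 2/6: 0.04-0.78; 3/6: 0.12-0.88; 4/6: 0.22-0.96 |
| 8 | 2/8: 0.03-0.65; 3/8: 0.09-0.76; 4/8: 0.16-0.84; 5/8: 0.24-0.91 |
| 10 | 3/10: 0.07-0.65; 4/10: 0.12-0.74; 5/10: 0.19-0.81; 6/10: 0.26-0.88 |
| 12 | 3/12: 0.05-0.57; 4/12: 0.10-0.65; 5/12: 0.15-0.72; 6/12: 0.21-0.79; 7/12: 0.28-0.85 |

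Add one line to Section 8.2.1.2: the 95% confidence interval for the Part 2 primary endpoint will be Clopper-Pearson.

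The cost is one table, one sentence and one added line. Design, sample size and the 50% statement stay as they are. The downside is that Clopper-Pearson is conservative (coverage 96-99% at n=12 for true rates of 24.5-60%), with higher upper limits at low counts, for example 0.65 instead of 0.60 at 4/12. Another small-sample method would also close the gap, provided it is named before the analysis and the table is recomputed with it.
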